This will be a randomized, blinded, prospective study with 2 groups; placebo group and supplemented group with 22:6n-3. Women will be enrolled and randomized by 16 weeks gestation. An initial dietary assessment will be done and blood will be collected at 16 weeks. The dietary supplementation will then commence and continue until delivery. The dietary assessment and maternal blood sample will be repeated at 36 weeks gestation. Hospital registration charts will be marked to indicate the women who are participants in this research, and will contain a copy of the informed consent. Following delivery, fetal cord blood and umbilical cord tissue will be collected. Length of gestation, newborn infant weight, length, head circumference and gender will be recorded. The mother-infant pairs will be followed for 18 months following delivery.

To account for drop-outs, approximately 200 mothers per group will be randomized in order to have 120 participants per group.

II. Primary/Secondary Endpoints

Primary: Infant CNS maturity

Secondary: language development, sleep-wake cycle and crying behavior, cognitive and behavioral development, growth (weight, length, head circumference), maternal lipid and fatty acid analysis, gestation length and incidence of prematurity.

Selection of participants

I. Study population:

Acceptable participants will be identified from the registrations for low-risk delivery at the BC Women's Hospital and through advertising. Eligible participants will be 20-40 years of age, 12-16 weeks gestation, expected to deliver a single full-term (37-42 weeks) infant.

II. Participant Exclusion Criteria

All mothers:

- Diabetes
- Cardiac disease
- Renal disease
- Tuberculosis
- HIV/AIDS
- Hepatitis
- Previous pregnancy complications
- Substance abuse

III. Randomization

Participants will be randomized to the supplements using a random number system. The supplements will be given as 2x500mg capsules of single cell triglycerides to provide about 400 mg 22:6n-3, or soybean/corn oil as a placebo. The supplements and placebo capsules will be provided in prepackaged sealed containers for dispensing and will both contain an orange flavor to assist in further blinding. The capsules will be dispensed at 16, 26 and 36 weeks. The number of capsules remaining in each vial will be recorded, and used with the number dispensed, to calculate the number taken by each subject.

Investigational Plan

Study Procedures and Observations

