Study visits will occur when the participants are at 16 and 36 weeks gestation, and at 1, 2, 3, 6, 9, 12, 14 & 18 months postpartum.

Study visit 1 (16 weeks gestation)

- Informed consent – At or prior to this visit, the participant who meets all of the applicable inclusion criteria and none of the exclusion criteria will be contacted and the study will be explained to them. Their questions will be answered to their satisfaction. After giving time for consideration, the participant will be asked to grant permission for their infant and themselves to participate in the study. If permission is granted, an informed consent form will be signed by the participant and a copy of the signed consent written informed consent form will be provided to them.
- Verify inclusion and exclusion criteria.
- Randomization.
- Dispense supplements.
- Dietary assessment (Food frequency of prior 4 weeks + weighed 3 day food record)
- Maternal blood sample.

Study days 16 – 36 weeks gestation

- Periodic phone calls to participant.
- Dispense supplements.

Study visit 2 (36 weeks gestation)

- Dietary assessment (Food frequency of prior 4 weeks + weighed 3 day food record).
- Maternal blood sample.
- Dispense supplements.

Study days 36 weeks gestation – Day of delivery

- Periodic phone calls to participant.

Day of delivery (37 – 42 weeks gestation)

- Fetal cord blood collection.
- Anthropometric measurements of newborn (body weight, body length and head circumference).
- CNS maturation measures at 48-72 hr (EEG and ABR).

Study visit 3 (1 month postpartum)

- Breast-milk collection (breast-feeding mothers).
- Anthropometric measurements of infant (body weight, body length and head circumference).
- Infant feeding diary.

Study visit 4 (2 months postpartum \pm 2 days)

- Breast-milk collection (breast-feeding mothers).
- Anthropometric measurements of infant (body weight, body length and head circumference).
- Looking acuity assessment.
- Infant feeding diary.

Study visit 5 (3 months postpartum \pm 2 days)

- Breast-milk collection (breast-feeding mothers).
- Anthropometric measurements of infant (body weight, body length and head circumference).
- CNS maturation measures (EEG and ABR).
- Looking acuity assessment.
- Infant feeding diary.

Study months 4 & 5 postpartum

- Infant feeding diary.
- Periodic phone calls to participant.

Study visit 6 (6 months postpartum \pm 2 days)

- Anthropometric measurements of infant (body weight, body length and head circumference).

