Body length at birth will be obtained from the infant's birth records or directly from the parent/care giver, if the record is not available to the Investigator.

Body length for the study period will be measured 1 time at each visit to the nearest millimeter. The infant should be held in a recumbent position with the help of two examiners and a suitable measuring device. One person holds the infant's head into contact with the fixed headboard and a second person holds the infant's feet, toes pointing directly upward and while applying gentle traction, bring the movable footboard to rest firmly against the infant's heels.

7) Head circumference

Head circumference at birth will be obtained from the infant's birth records or directly from the parent/care giver, if the record is not available to the Investigator.

Head circumference for the study period will be measured 1 time at each visit to the nearest millimeter employing a flexible, non-stretchable cloth or vinyl tape. The tape is to be applied firmly around the head above the supraorbital ridges, covering the most prominent part of the frontal bulge anteriorly, and over the part of the occiput that gives maximum circumference.

8) Periodic phone calls

Study personnel will contact the participants periodically between study visits to collect information on diet, tolerance, and adverse events, determine if additional supplements are needed, remind participants of upcoming study visits, and answer questions concerning the study.

9) Maternal dietary intake/Infant dietary intake

At study visits 1 & 2, participants will be asked to complete a food frequency questionnaire of the preceding 4 weeks, together with a weighed 3-day food record. The food frequency questionnaire will be completed using an interview format with a trained dietician, using food models, scales, cups and spoons. Information on the frequency with which the food is eaten, portion size, brand name or place of purchase, methods of preparation, types of margarine, fats and oils, and types of fish and seafood will be collected.

Infant dietary intakes will be recorded using a feeding diary completed each month, and designed to capture when human milk is substituted, juices and solids are introduced and what they are. At study visits 7 and 10, dietary intake will be collected using an infant food frequency questionnaire.

10) Final evaluation

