This form will document if the participants completed the study (visit 10) and if not, the reason for withdrawing from the study including the date of the last study visit.

Investigational product

The study supplements for the participants enrolled in this study will be provided in a capsule form.

These study supplements will be supplied by Martek Bioscience Corp:

- Single cell triglyceride capsules to provide about 400mg 22:6n-3.
- Soybean/corn oil as placebo capsules

The 22:6n-3 and placebo capsules will be provided in prepackaged sealed containers for dispensing. The participants will be randomized to the supplements using a random code number system. The study supplements will contain an orange flavor to assist in further blinding. The number of unused capsules will be recorded at 26 weeks gestation, 36 weeks gestation and after delivery in order to calculate the total number taken by each subject.

Duration of use

Study supplement usage is from 16 weeks gestation to day of delivery.

Statistics

Sample size

The calculation of sample size is based on the measures of CNS maturity of language development, VEP visual acuity and Bayley Scales, rather than the biochemical determinants, which will require a smaller sample size of <30 per group. Sample sizes were estimated for VEP acuity, language development at 9 and 14 months using the non-native consonant recognition and CDI, and Bayley Scales at 18 month. EEG was not included since there is no baseline information on which to estimate the difference or variability. Taking into account the multiple outcomes using the Bonferroni correction, the largest sample size required is 120/group with a corrected α of 0.05 and power of 80% to detect an effect size equal to half a standard deviation.

Statistical analysis

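### As written, nobody asks about adverse events from delivery through the 3-month visit: the only stated route is phone calls, and none is scheduled until months 4 and 5

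*Protocol*

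**What the plan says.** **How adverse events are collected.** Methods to assess study endpoints, item 8 (Periodic phone calls), is the only place in the protocol that mentions them: "Study personnel will contact the participants periodically between study visits to collect information on diet, tolerance, and adverse events".

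**When the calls occur.** Study Procedures and Observations lists calls block by block. The last block before birth is "Study days 36 weeks gestation – Day of delivery", whose only entry is the calls. The first after birth is "Study months 4 & 5 postpartum".

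**What happens in between.** The delivery entry has cord blood, newborn measurements and "CNS maturation measures at 48-72 hr (EEG and ABR"). The next entries are "Study visit 3 (1 month postpartum"), "Study visit 4 (2 months postpartum" with its two-day window) and the 3-month visit. Their items are milk samples, body measurements, feeding diaries, looking acuity (2 and 3 months) and EEG/ABR (3 months).

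**What is recorded at birth.** Study design, I: "Length of gestation, newborn infant weight, length, head circumference and gender will be recorded". Incidence of prematurity is a secondary endpoint.

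**When exposure ends.** Duration of use: "Study supplement usage is from 16 weeks gestation to day of delivery".

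**The concern.** The women take the supplement during pregnancy for the infant's benefit. Labour, delivery, the newborn stay and early infancy are the periods in which an unwanted effect of that exposure on mother or child could most readily be noticed. These are also the periods in which the schedule has nobody asking. Questioning stops on the day exposure stops and resumes months later.

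Two things follow if the plan is carried out as written. A perinatal event enters the record only if the mother recalls it at a call months afterwards, or volunteers it at a visit where staff have no stated instruction to ask. A mother who leaves follow-up between birth and the first postpartum call is never asked about the birth or what followed. The final form would give her reason for leaving but no event history. No analysis can recover events that were never asked about.

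**Working it through.** The protocol gives no figure to reproduce, so the check is a reading of every schedule entry for two things: a phone call, or an adverse-event or tolerance item.

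| Schedule entry | Call listed | Adverse-event item |
|---|---|---|
| Visit 1 (16 weeks) | no | no |
| 16 to 36 weeks | yes | by phone |
| Visit 2 (36 weeks) | no | no |
| 36 weeks to delivery | yes | by phone |
| Delivery, with 48-72 hr measures | no | no |
| Visit 3 (1 month) | no | no |
| Visit 4 (2 months) | no | no |
| Visit 5 (3 months) | no | no |
| Months 4 and 5 | yes | by phone |
| Visits 6 to 10 | no | no |
| Months 7-8, 10-11, 13, 15-17 | yes | by phone |

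1. **Call blocks.** There are 2 before birth and 5 after, 7 in all. The five postpartum blocks cover 2 + 2 + 2 + 1 + 3 = 10 calendar months: 4, 5, 7, 8, 10, 11, 13, 15, 16 and 17.
2. **Adverse-event items.** 0 of 10 visits and 0 of 1 delivery entries have one.
3. **Length of the gap.** It opens on the day of delivery. The next call block follows the 3-month visit, so the gap is at least about 3 months. If month 4 is taken to start at three completed months and month 5 to end at five, the first question about an event at birth comes roughly 3 to 5 months after it, depending on when in the block the call is made.
4. **Other forms that might fill the gap.**
   - The final evaluation (item 10) records completion, the reason for withdrawal and the date of the last visit.
   - The capsule count after delivery (Investigational product) carries no safety question.
   - The feeding diary covers diet only.
   - The birth data cover gestation length, size and gender.

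   None of these asks about adverse events in general.
5. **What is covered.** Capsules run from 16 weeks to delivery, and calls are listed in both blocks that make up that period. Tolerance while taking capsules therefore has a stated route.

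**The case against.** The strongest reply is that the two parts of the protocol are compatible. Item 8 speaks of periodic calls between visits and does not promise one in every interval. The postpartum calls fall exactly in the months without a visit, while months 1, 2 and 3 each have one, so the calls look designed to fill in where nobody is seen. This stands. A reader might infer that the schedule contradicts item 8, and the text does not support that. But if visits replace calls in those months, the one stated route for adverse events goes with the calls, because no visit takes it over.

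A second reply is that the visit list is not exhaustive. It omits umbilical cord tissue, the 2-month infant blood sample, the sleep/wake records and the capsule counts, all stated elsewhere. So a missing line is not proof that nothing is asked. That is fair, but the omitted procedures do appear somewhere else in the protocol. Adverse-event questioning at delivery or at visits 3 to 5 appears nowhere. No visit record form is described, so one cannot say that volunteered events would have no place to be written down. One can say only that nothing directs staff to ask.

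Three further limits stand:

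- **Newborn outcomes.** It is tempting to say that newborn events go unrecorded. Gestation length, prematurity and birth size are measured in both arms, and infant size again at 1, 2 and 3 months.
- **Attrition.** The planned fall from about 200 to 120 per group has no stated timing, so it does not show how many mothers would be lost before month 4.
- **Analysis.** No endpoint or analysis in the protocol compares adverse events between arms, so no planned result is spoiled.

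An unseen SAP would not settle the point: when and how events are asked about is a matter for the protocol.

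**Conclusion.** The gap in ascertainment is real and of limited size. From the day of delivery through the 3-month visit, the plan as written asks no mother about adverse events in herself or her infant, other than the prematurity, gestation length and birth size recorded as outcomes. The first question comes roughly 3 to 5 months after birth. Questioning is then scheduled in ten later calendar months, all further from exposure.

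This rests on two assumptions. The first is that staff follow the schedule and item 8 as they read; informal questioning at the early visits would narrow the gap, but nothing requires it. The second is the reading of the month labels given in the check.

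The efficacy endpoints and their analysis are untouched. A reader might go further and infer that the supplement's tolerability is unassessed. The documents do not support this, since calls are scheduled throughout dosing. The point is a cheap improvement to safety data that cannot be repaired afterwards.

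**What to change.** Add a short adverse-event item, asked in the same way in both arms by blinded staff and covering the time since the last contact, to:

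- the existing contact after delivery, either the 48-72 hr EEG/ABR session or the capsule count;
- visits 3, 4 and 5 (1, 2 and 3 months).

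Then state in item 8 that adverse events are collected at these contacts as well as by phone. Collection would run without a break from the first capsule to the month 4 and 5 calls, which stay as they are.

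Birth records are already consulted for newborn weight, length and head circumference, and can support the post-delivery item where available. A full extract of maternal and newborn events from the hospital chart is optional. It would be new work: the protocol has charts marked to show participation and to hold the consent, but does not describe extracting events from them.

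The cost is a few minutes at each of four existing contacts and more event records to review. No new visit is needed.

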The Bayley Scales of Infant Development II, a standardized test of infant development, will be given at 18 months postpartum, with the mental development index (MDI) and psychomotor development index (PDI) standardized for age, based on reference norms. The MDI score is derived from the total number of items correctly performed, regardless of skill or weakness in any particular area. The Bayley Scales II, however, includes clusters of items (Facets) for the mental scale that provides information on language, cognitive and visual-motor abilities. Scores for each facet will be quantified as the ratio of correct items to the total number of items in the Facet as described by [name]. Scores on the Facets at 18 months of age are related to cognitive, verbal and visual-motor function at 4 – 5 years of age assessed with the Wechsler Preschool and Primary Scale of Intelligence. Dr. [name], who has extensive experience with the Bayley Scales, will collaborate. The test will be given by a trained tester, with equipment and procedures. We will test at 18 months because the range of tasks that can be completed is greater than at younger ages, thus allowing a greater sensitivity to discriminate differences among infants.

4) Blood, tissue and milk samples

Blood will be drawn via venipuncture for a fatty acid profile from all mothers at 16 and 36 weeks gestation. A total of 3.0 ml of blood is needed for each blood draw. Fetal cord blood will be collected following delivery of the infant.

Breast-milk samples will be collected from all breast-feeding mothers at 1 and 2 months postpartum. The mothers will be instructed not to collect milk during the first 2 – 5 minutes of a feed (fore-milk), or drip milk, then interrupt the infant and gently express about 10 ml of human milk into the vial provided. The mother should label the vial with the date the sample was obtained. Samples will be frozen following collection, transported on ice and stored at -80 C on receipt at the lab.

5) Body weight

Birth weight will be obtained from the participant's birth records or directly from the parent/care giver, if the record is not available to the Investigator.

During the study period, infants will be weighed one time at each visit without clothing or diaper, on a standard pediatric balance, to the nearest gram. All balances will be checked to register the same weights throughout the range of weights expected.

6) Body length

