Differences in maternal plasma, RBC, fetal umbilical cord plasma and RBC and milk fatty acids between the 2 randomized groups will be determined using one way analysis of variance (ANOVA). One way ANOVA will be used to test for differences in measures of CNS maturity, looking acuity, and language development. Regression analyses will be used to determine the relation between intake (g/day & adjusted for energy intake) of selected fatty acids and the maternal and infant blood, umbilical tissue and milk 20:4n-6, 20:5n-3 and 22:6n-3. A stepwise multiple regression will be used to predict independent factors, including gender, maternal smoking and alcohol intake (as appropriate), highest level of education attained by the mother, family income, birth order, ethnic background, and maternal weight gain in pregnancy, maternal dietary

variables, and duration of breast-feeding, associated with the developmental outcomes. The measures of weight, length and head circumference will be used to plot growth curves for each infant, then an imputation procedure used to estimate weight, length, head circumference and rate of growth from birth to exactly 4, 6, 9 and 18 month for each infant.

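### 36-week maternal plasma and RBC fatty acids are compared by one-way ANOVA without each woman's 16-week pre-supplement value: a valid analysis, but less precise than the data allow

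*Protocol*

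**What the plan says.** The protocol, under Statistics, Statistical analysis, takes as its subject "Differences in maternal plasma, RBC, fetal umbilical cord plasma and RBC and milk fatty acids between the 2 randomized groups" and fixes the method in the same sentence: "milk fatty acids between the 2 randomized groups will be determined using one way analysis of variance (ANOVA"). The sentence covers maternal plasma and RBC, cord plasma and RBC, and milk. It names neither a covariate nor a time point.

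The baseline is described elsewhere. Study design, Description of study: "An initial dietary assessment will be done and blood will be collected at 16 weeks", and then "The dietary supplementation will then commence and continue until delivery". Methods to assess study endpoints, item 4: "Blood will be drawn via venipuncture for a fatty acid profile from all mothers at 16 and 36 weeks gestation". The visit lists for 16 and 36 weeks both include the entry "Maternal blood sample".

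Two statements bear on the weight of the point. The secondary endpoints include "maternal lipid and fatty acid analysis, gestation length and incidence of prematurity". The Sample size section bases the trial's size on the developmental measures, "rather than the biochemical determinants, which will require a smaller sample size of <30 per group".

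**The concern.** A woman's fatty acid status before the first capsule may well predict her status 20 weeks later. One-way ANOVA by group has no term for it. Two things follow. Variation between women that was already present at 16 weeks stays in the residual and widens the interval. And if the groups happen to differ at 16 weeks, the correlated part of that difference carries into the 36-week estimate.

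The other analyses in the section do not fill the gap. One regression relates fatty acid intake to blood, tissue and milk levels. The stepwise model concerns developmental outcomes, and its listed factors do not include the 16-week fatty acid value. Neither is an analysis of the randomized fatty acid contrast.

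This contrast shows whether supplementation raised maternal 22:6n-3, which is the first step in interpreting any developmental difference. It is worth estimating as precisely as the collected data permit.

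**Working it through.** **Inputs from the protocol.** 120 per group planned after drop-out; power 80%; fewer than 30 per group said to be enough for the biochemical measures. **Assumed.** Two-sided α of 0.05 for a single comparison (sidedness is not stated); equal SDs in the two groups; r from 0.3 to 0.7, because no correlation is given.

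**1. The plan's own figure.** The figure of fewer than 30 per group cannot be reproduced, because no effect size or SD is given for it. Working backwards with the normal approximation, 30 per group corresponds to

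d = (1.960 + 0.842) × √(2/30) ≈ 0.72 SD.

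**2. Unadjusted power at 120 per group.** Power = Φ(d × √(120/2) − 1.960).

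- d = 0.72: 99.99%
- d = 0.5: 97.2%

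The effect detectable with 80% power is (1.960 + 0.842) × √(2/120) = 0.362 SD.

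**3. Effect of adjustment.** With the 16-week value as covariate, the residual SD becomes SD × √(1 − r²), so the variance of the group difference is multiplied by 1 − r². The unadjusted sample size with the same precision is 120/(1 − r²).

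| Assumed r | Variance | SE | 120 per group acts like | Detectable effect, 80% power |
|---|---|---|---|---|
| 0.3 | −9% | × 0.954 | 132 | 0.345 SD |
| 0.5 | −25% | × 0.866 | 160 | 0.313 SD |
| 0.7 | −49% | × 0.714 | 235 | 0.258 SD |

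Over a wider range of r, 0.2 to 0.8, the variance reduction runs from 4% to 64%. For an effect of 0.5 SD, adjustment at r = 0.5 raises power from 97.2% to 99.4%.

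**4. Chance imbalance.** The standard error of a baseline difference, in SD units, is √(2/120) = 0.129. If the groups differ at 16 weeks by one such standard error, and the SDs at the two times are equal, the unadjusted 36-week difference is expected to shift by r × 0.129: 0.039, 0.065 or 0.090 SD for r = 0.3, 0.5 or 0.7. ANCOVA removes this shift.

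**The case against.** The strongest reply is that nothing here is wrong. Randomization makes one-way ANOVA unbiased, and its standard error already allows for chance imbalance. The endpoint is secondary, and by the protocol's own figure the trial is at least four times larger than this endpoint needs (120 against fewer than 30). The size of the gain rests on a correlation that the documents do not supply. Covariates are often left to a statistical analysis plan, which is not at hand.

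Most of this stands. A reader might infer that the planned comparison is biased or underpowered; the protocol supports neither reading. The last part does not defeat the point: the protocol does not leave the method open but names an unadjusted one.

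Three further limits apply.

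- **Number analysed.** The 120 per group allows for drop-outs from about 200 randomized per group, with follow-up to 18 months, so more women may have a 36-week sample. The percentage reductions in variance do not depend on this; the equivalent sample sizes do.
- **Cord blood and milk.** A reader might expect the same gain there. Neither has a baseline of its own, and milk is collected after supplementation has ended. The maternal 16-week value is a legitimate covariate, but its correlation with these outcomes is probably lower.
- **Tests at 16 weeks.** A reader might infer that the ANOVA will also be run on the 16-week samples. Objective VII mentions comparing maternal blood from both times, but that wording is ambiguous and the Statistical analysis section names no time points. The documents do not establish such a test.

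**Conclusion.** The point holds as a free improvement in efficiency. The protocol specifies an unadjusted comparison of the maternal fatty acids while collecting a pre-supplement value of the same quantity from every mother, and no analysis of the randomized contrast uses that value. The wording of the plan is clear; the size of the gain is uncertain. For an assumed r of 0.3, 0.5 or 0.7 the variance of the group difference would fall by 9%, 25% or 49%. The benefit is narrower intervals and protection against chance imbalance. Since power is already ample by the protocol's own figures, the change is unlikely to alter whether a difference is declared. The case is firm for 36-week maternal plasma and RBC, and weaker for cord blood and milk.

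**What to change.** In the Statistical analysis section, replace one-way ANOVA for the 36-week maternal plasma and RBC fatty acids with a prespecified ANCOVA. Each model has randomized group and the 16-week value of the same fatty acid in the same compartment (plasma with plasma, RBC with RBC). Report the adjusted group difference with its confidence interval.

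For cord blood and milk, the maternal 16-week value may be named as a covariate. If so, state in advance which maternal compartment is used.

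The cost is a change of wording and one degree of freedom per model, out of 2 × 120 − 2 = 238. No extra sample, visit or measurement is needed. The choice should be fixed before unblinded data are seen.

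### The supplement effect is tested by unadjusted ANOVA although prognostic baseline factors are already planned as regressors; the stepwise regression that uses them cannot stand in as an adjusted estimate

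*Protocol*

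**What the plan says.** All references are to the protocol.

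- **Group test (Statistical analysis).** "One way ANOVA will be used to test for differences in measures of CNS maturity, looking acuity, and language development". No covariates are mentioned. The endpoints section gives "Primary: Infant CNS maturity", so this test covers the primary endpoint.
- **Regression (same paragraph).** "A stepwise multiple regression will be used to predict independent factors, including gender, maternal smoking and alcohol intake (as appropriate"). The list goes on through maternal education and family income to "birth order, ethnic background, and maternal weight gain in pregnancy, maternal dietary" "variables, and duration of breast-feeding, associated with the developmental outcomes". Randomised group is not among the named factors. No entry or removal threshold is given.
- **Timing (Description of study).** "Women will be enrolled and randomized by 16 weeks gestation". On maternal diet: "The dietary assessment and maternal blood sample will be repeated at 36 weeks gestation". The regression does not say whether the 16-week or the 36-week dietary data are meant.
- **Prognostic information.** The MacArthur CDI section notes that girls tend to be slightly ahead. It scores the CDI both as a raw word count and as percentiles by age and gender. The Bayley indices are standardised for age.

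**The concern.** The paragraph holds two separate analyses, and neither makes good use of the baseline factors.

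The ANOVA answers the randomised question but leaves out factors that the plan itself regards as likely predictors of development. In a randomised trial that costs precision, not validity.

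The regression uses those factors but does not address the randomised question as written. Maternal weight gain in pregnancy arises mostly after randomisation, and duration of breast-feeding wholly after it. Maternal diet does so too if the 36-week record is used. If group were added to such a model, conditioning on these variables could remove or distort part of the supplement effect. Stepwise P values are also calculated as if the final model had been fixed in advance, so some reported independent factors will be chance findings.

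At stake are some power in the main comparisons, and the risk that the regression is later read as the adjusted result.

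**Working it through.** **1. The plan's own figure.** Inputs from the Sample size section: 0.5 SD, 80% power, 120 per group and a corrected alpha of 0.05. The number of comparisons and the sidedness are not given; I take two-sided tests.

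n per group = 2(z₁₋α/₂ + z₀.₈)² / 0.5²

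- alpha 0.05: 63
- alpha 0.05/4 = 0.0125 (four outcomes): 90
- alpha 0.05/20 = 0.0025: 120

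The stated 120 is therefore not reproduced at a literal 0.05. It corresponds to a per-test level near 0.0025, which is back-solved and not stated. Because the level is unclear, step 2 shows all three.

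**2. Precision from baseline covariates.** If covariates explain a share R² of outcome variance, the effect in residual SD units is d = 0.5/√(1 − R²), and the equivalent sample size is 120/(1 − R²). R² of 0.10 to 0.20 is my assumption; the protocol gives no value.

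- R² = 0: d = 0.500, noncentrality 0.500 × √60 = 3.873
- R² = 0.10: d = 0.527, noncentrality 4.082, equivalent n = 133
- R² = 0.20: d = 0.559, noncentrality 4.330, equivalent n = 150

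Power from the noncentral t distribution on 238 degrees of freedom, ignoring the few degrees of freedom spent on covariates:

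| Two-sided alpha | R² = 0 | R² = 0.10 | R² = 0.20 |
|---|---|---|---|
| 0.05 | 97% | 98% | 99% |
| 0.0125 | 91% | 94% | 96% |
| 0.0025 | 79% | 85% | 90% |

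**3. False selections.** With m independent null candidates and entry at P < 0.05 (threshold assumed), the chance of at least one false selection is 1 − 0.95^m.

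- m = 5: 23%
- m = 10: 40% (a simulation with 240 infants and removal at P > 0.10 also gave 40%)

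The protocol names about ten candidates. If five are truly prognostic, the five-null figure is the relevant one unless the dietary item brings in many variables.

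**4. Adjusting for a post-randomisation variable.** This is an illustration under assumed values, with a total supplement effect of 0.50 SD. If a variable carrying 0%, 25% or 50% of that effect is added beside group, the group coefficient averages about 0.50, 0.37 or 0.25. The protocol does not say that it will fit such a model; this shows only why the listed factors are unsuitable for one.

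**The case against.** The strongest reply is that the protocol never presents the regression as covariate adjustment. It looks for factors associated with the developmental outcomes, while a separate ANOVA tests the supplement. That stands. A reader might infer that the trial's adjusted supplement effect will come from a stepwise model that leaves out group and is biased by post-randomisation variables. The text does not support this: no adjusted supplement effect is announced, the ANOVA is untouched by the regression, and the list opens with 'including', so group is unnamed but not excluded. Breast-feeding duration and diet are also reasonable candidates in an association analysis.

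A second reply is that choosing ANCOVA over ANOVA is a matter of efficiency, and that covariate sets are often left to an analysis plan, which is not at hand here. This too is largely right, and no error is alleged in the ANOVA. The protocol does, however, fix the test and name the predictors, so it is fair to say that the two could be joined at little cost.

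Third, the precision argument is partly met already. CDI percentiles account for age and gender, and the Bayley indices for age, so the gain is smaller for those scores. It remains open for raw word counts and for the electrophysiological and acuity measures.

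A reader might also infer that Bayley and behavioural outcomes would be compared only through the regression, because the ANOVA sentence does not name them. Their group test may be specified in an analysis plan not shown, so that inference goes too far.

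**Conclusion.** The point holds as an improvement, not as a flaw that invalidates the trial's inference. The group test for CNS maturity, looking acuity and language is valid but forgoes precision from baseline factors that the plan already intends to analyse. As described, the stepwise regression is exploratory and cannot serve as an adjusted supplement estimate.

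The size depends on unstated quantities. With an assumed R² of 0.10 to 0.20, the gain is one to two percentage points of power at alpha 0.05, three to five at 0.0125, and about six to eleven at the back-solved 0.0025. The chance of a false stepwise selection, 23% to 40%, rests on independent candidates and an assumed entry level.

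**What to change.** - Make each between-group comparison an ANCOVA with group forced in and a short prespecified set of baseline covariates: infant sex, maternal education, birth order and ethnic background.
- State that the regression on developmental outcomes is exploratory. Replace stepwise selection with a fixed model reported with confidence intervals.
- State that pregnancy weight gain, breast-feeding duration and 36-week diet will not be used to adjust the supplement effect, and say which dietary assessment the regression uses.

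The cost is mainly wording. Infant sex is already recorded at delivery. The other three covariates are planned regressors, but the visit schedule does not list when they are collected, so their collection at enrolment should be confirmed.
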